IGT Systems	Post-Market Clinical Study Protocol DCR4Contrast Clinical Evidence Study	Doc ID: XCY612-130576 Rev: 02 Page 1 of 33
-------------	-----------------------------------------------------------------------------	--------------------------------------------------

DCR4Contrast trial

Author:

[REDACTED] Development Scientist

Department:

Clinical Science & Medical Affairs

Approval

Name	Role	Date (yyyy Mon dd)	Signature
[REDACTED]	GEN: Clinical Operations Lead	2019 Jul 09	[REDACTED]
[REDACTED]	InCs: Study Leader	2019 Jul 09	[REDACTED]
[REDACTED]	Q&R: RA Officer	2019 Jul 09	[REDACTED]
[REDACTED]	GEN: Biostatistician	2019 JUL 09	[REDACTED]

All approvers have signed. Approval and effective date is the date of the latest signature.

IGT Systems	Post-Market Clinical Study Protocol DCR4Contrast Clinical Evidence Study	Doc ID: XCY612-130576 Rev: 02 Page 2 of 33
-------------	-----------------------------------------------------------------------------	--------------------------------------------------

Revision History

Revision	Revision Date	Author	Changes/Comments
00	2018 Apr 05		Initial version
01	2019 Jun 05		
Protocol updated based on feedback from investigators and study coordinators at the potential sites:
 
 • Target patient population extended from elective PCI to elective + ad hoc PCI; rephrased inclusion/exclusion criteria, objectives, endpoints and study procedures to accommodate this change (see Summary section, Chapter 5, 6, and 7) • Chapter 9: Changed such that all (also non significant) changes of the clinical study protocol shall be notified to, or approved by the MEC and where appropriate regulatory authorities. • Appendix I: Updated list of investigators, sites, and third parties involved in the study • Appendix II: Updated list of monitors/clinical scientists, clinical study managers
02	2019 Jul 04		
Protocol updated based on FDA pre-submission meeting feedback:
 
 • The secondary objective on the iodinated contrast volume used per vessel PCI has been moved to the Exploratory objectives. • Updated the sample size justification for the secondary objective resulting in 394 subjects required for the study (360 previously). • Added site effect analysis for the primary endpoint to assess poolability of data. • Added sensitivity analysis for the primary endpoint to perform worst-case analysis for missing data.

Open Issues

None

1.1. Purpose

This document is intended to be used as a template for the Post-Market Clinical Study Protocol for clinical studies. The document describes the minimum amount of information to be included in this clinical study protocol based on the regulations.

1.2. Scope

This post-market study protocol applies to the clinical evidence study Dynamic Coronary Roadmap for Contrast Reduction (**DCR4Contrast trial**).

1.3. References

Reference	Identification	Title / additional remarks
[CER]	DHF287327	Clinical Evaluation Report Dynamic Coronary Roadmap
[IFU]	4522 203 59903	IFU Dynamic Coronary Roadmap R2.0
[FDA]	K172307	FDA 510(k) clearance Dynamic Coronary Roadmap R2.0

The following documents that are not controlled by Philips are referred to in this document:

[MEDDEV]	MEDDEV 2.7/1	MEDDEV 2.7/1 rev 4 - Clinical Evaluation: a guide for manufacturers and notified bodies under directives 93/42/EEC and 90/385 EEC
[MDD]	EU MDD 93/42/EEC	Council Directive 93/42/EEC concerning medical devices. Amended by Medical Device Directive as amended by 2007/47/EC
[MDR]	EU MDR 2017/745	Regulation (EU) 2017/745 of the European Parliament and of the Council of 5 April 2017 on medical devices
[ISO14155]	EN ISO 14155	EN ISO 14155:2011 – Clinical Investigation of medical devices

IGT Systems	Post-Market Clinical Study Protocol DCR4Contrast Clinical Evidence Study	Doc ID: XCY612-130576 Rev: 02 Page 6 of 33
-------------	-----------------------------------------------------------------------------	--------------------------------------------------

1.4. Definitions & Abbreviations

Term	Description
AF	Atrial Fibrillation
AK	Air Kerma
AKI	Acute Kidney Injury
AKI-D	AKI requiring dialysis
AKIN	Acute Kidney Injury Network (definitions)
C(I)N	Contrast (Induced) Nephropathy
CABG	Coronary Artery Bypass Grafting
CE	Conformité Européenne (European Conformity)
CFR	Code of Federal Regulation
CI	Confidence Interval
CI-AKI	Contrast Induced AKI
CKD	Chronic Kidney Disease
CRF	Case Report Form
CRO	Contract Research Organization
DAP	Dose Area Product
DCR	Dynamic Coronary Roadmap
eCRF	Electronic Case Report Form
eGFR	estimated Glomerular Filtration Rate
eGFR	Estimated Glomerular Filtration Rate
FDA	Food and Drug Administration
FFR	Fractional Flow Reserve
GFR	Glomerular Filtration Rate
HTA	Health Tech Assessment
IDMS	Isotope Dilution Mass Spectrometry
iFR	instantaneous wave-Free Ratio
IFU	Instructions for Use
IQR	Interquartile Range
IRB	Institutional Review Board
ISO	International Organization for Standardization
ISR	In-Stent Restenosis
IVUS	IntraVascular UltraSound
LMCA	Left Main Coronary Artery
MDD	Medical Device Directive
MDR	Medical Device Reporting
MEC	Medical Ethic Committee
MI	Myocardial Infarction
MVD	Multi Vessel Disease
NRD	Nephropathy requiring dialysis
NSTEMI	Non-ST segment Elevation Myocardial Infarction
NYHA	New York Heart Association classification
OCT	Optical Coherence Tomography
PCI	Percutaneous Coronary Interventions
RCA	Right Coronary Artery
SCr	Serum Creatinine
SD	Standard Deviation
TIMI	Thrombolysis In Myocardial Infarction
UA	Unstable Angina

IGT Systems	Post-Market Clinical Study Protocol DCR4Contrast Clinical Evidence Study	Doc ID: XCY612-130576 Rev: 02 Page 7 of 33
-------------	-----------------------------------------------------------------------------	--------------------------------------------------

2. Summary

Identification of study device

The Dynamic Coronary Roadmap is a commercially available (CE labeled, FDA 510(k) cleared: K170130 for Dynamic Coronary Roadmap R1, and K172307 for Dynamic Coronary Roadmap R2) product developed by Philips Medical Systems, a Philips Healthcare company. Dynamic Coronary Roadmap is a software medical device intended to provide a real-time and dynamic angiographic roadmap of coronary arteries. The angiographic roadmap is automatically generated from previously acquired coronary angiograms during the same procedure. Dynamic Coronary Roadmap overlays the angiographic roadmap on live 2D fluoroscopic images, thereby assisting the physician in navigating devices, e.g. (guide) wires, catheters, through the coronary arteries.

Dynamic Coronary Roadmap is to be used in combination with a Philips interventional X-ray system.

Study design

This is a multi-center, prospective, unblinded, stratified 1:1 randomized controlled trial to assess whether using Dynamic Coronary Roadmap reduces the total iodinated contrast volume related to PCI compared to the control group without Dynamic Coronary Roadmap. In the randomization process all subjects within each type of PCI (ad hoc or elective) will be stratified according to the number of vessels to be treated via PCI, i.e., 1, 2, or 3 or more vessel PCI.

Objectives

Primary objective:

- To assess whether using Dynamic Coronary Roadmap reduces the total iodinated contrast volume related to PCI compared to the control group without Dynamic Coronary Roadmap.

Secondary objective:

- To assess the total number of contrast enhanced cine angiographic X-ray runs (angiograms) related to PCI in the Dynamic Coronary Roadmap and control group

Exploratory objectives:

- To assess the iodinated contrast volume used per vessel PCI in the Dynamic Coronary Roadmap and control group
- To assess the total iodinated contrast volume related to PCI per stratification group, i.e., 1 vessel PCI, 2 vessel PCI and 3 or more vessel PCI, in the Dynamic Coronary Roadmap and control group
- To assess the total iodinated contrast volume related to PCI in subgroups of simple, intermediate and complex PCI (where the SYNTAX score for the vessel(s) treated with PCI will be used as an index for complexity) in the Dynamic Coronary Roadmap and control group
- To assess the incidence of Acute Kidney Injury (AKI) in the Dynamic Coronary Roadmap and control group (at discharge following standard clinical care)
- To assess the variability of the total iodinated contrast volume related to PCI in the Dynamic Coronary Roadmap and control group
- To assess the total fluoroscopy & procedure time related to PCI in the Dynamic Coronary Roadmap and control group
- To assess the total X-ray dose (DAP, AK) related to PCI in the Dynamic Coronary Roadmap and control group
- To assess the procedural success in the Dynamic Coronary Roadmap and control group
- To register in-hospital Major Adverse Cardiovascular and Cerebral Events (MACCE) in the Dynamic Coronary Roadmap and control group

Primary and secondary endpoints

The primary endpoint of the study is the average total undiluted iodinated contrast volume (in ml) used per PCI (from first positioning the interventional guiding catheter in stable coronary position till end of PCI procedure) measured by an automatic contrast injector.

IGT Systems	Post-Market Clinical Study Protocol DCR4Contrast Clinical Evidence Study	Doc ID: XCY612-130576 Rev: 02 Page 8 of 33
-------------	-----------------------------------------------------------------------------	--------------------------------------------------

Secondary endpoint:

- The average total number of contrast enhanced cine angiographic X-ray runs (angiograms) per PCI (from first positioning the interventional guiding catheter in stable coronary position till end of PCI procedure) determined via visual assessment (e.g., on the Philips X-ray system).

Main inclusion criteria

- Subject is undergoing Percutaneous Coronary Intervention (PCI) with a degree of complexity that anticipates the need for more than 25ml of iodinated contrast volume
- Subject has signed informed consent
- Subject is 18 years of age or older, or of legal age to give informed consent per state or national law

Main exclusion criteria

- Subject undergoing emergency PCI
- Subject with ST-segment Elevation Myocardial Infarction (STEMI)
- Subject with Chronic Total Occlusion (CTO)
- Subject undergoing PCI for isolated ostial disease of Left Main Coronary Artery (LMCA) or Right Coronary Artery (RCA)
- Subject undergoing PCI with Optical Coherence Tomography (OCT) support
- Subject undergoing PCI with rotational or orbital atherectomy
- Subject with Chronic Kidney Disease (CKD) stage V (eGFR < 15 ml/min/1.73 m²)
- Subject with contrast allergy that cannot be adequately pre-medicated
- Subject participates in a potentially confounding drug or device trial during the course of the study.
- Subject is under 18 years of age, or pregnant woman, or breast feeding woman, or meets an exclusion criteria according to national law

No. of subjects

In total 394 subjects will be enrolled in the study during an expected enrollment period of 9 months.

Study procedures

Physician investigators participating in this study are expected to follow their normal clinical practice in treating and following up patients with Coronary Artery Disease (CAD). Patients randomized to the DCR group will undergo a PCI procedure during which DCR is used while those randomized to the control group will undergo PCI without the use of DCR. The preparation of the PCI procedure, the procedure itself and follow up will be performed following standard of care.

Screening

Patients scheduled for PCI will be screened on inclusion and exclusion criteria by the principal investigator or delegated and trained study personnel. When a patient is eligible study information and the informed consent form is provided to the patient and after providing ample time to consider participation the patient is asked for signed consent.

PCI procedure

The investigator will perform PCI using standard of care procedures.

Standard of care PCI entails (deviations allowed up to investigator's discretion):

→ **In case of elective PCI: Randomization before procedure**

- Arterial access (femoral or radial; preferably perform femoral angiography of preclose device at this moment)
- In case of ad hoc PCI: Diagnostic Coronary Angiography

→ **In case of ad hoc PCI: Randomization upon decision to go for PCI**

- First positioning of interventional guiding catheter in stable coronary position

→ **Record the contrast volume used up to that moment**

- Coronary Angiography **[DCR group: DCR started automatically]**
- Position guidewire

- Position balloon + inflate balloon
- Position stent + deploy stent
- Check PCI result by Coronary Angiography (potentially combined with e.g. Stent Boost, IVUS)
- Repeat above steps when necessary, e.g. post-dilate stent or perform PCI in different vessel
 - **Record the total contrast volume used**

The principal investigator or his delegates on the study team will enter data in a pre-designed e-CRF. This will include patient demographics, relevant past medical history, specific target CAD data along with pre-procedural/screening imaging details, PCI procedure data and follow-up data until patient discharge.

[figure not shown]

Figure 1 Clinical workflow of the DCR4Contrast trial following standard of care for PCI (ad hoc and elective)

Follow up

The subjects will be followed-up until discharge following standard clinical care.

Duration of the study

The total duration of the study is expected to take 9 months.

IGT Systems	Post-Market Clinical Study Protocol DCR4Contrast Clinical Evidence Study	Doc ID: XCY612-130576 Rev: 02 Page 10 of 33
-------------	-----------------------------------------------------------------------------	---------------------------------------------------

3. Device Description

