7.5. Demographics and Baseline Characteristics

Basic subject characteristics such as age, gender, height and weight will be summarized. In addition, the SYNTAX score [Sianos 2005, Neumann 2018] will be determined for the vessel(s) treated with PCI as an index for anatomical complexity, the number of lesions treated in the PCI, the location of the lesion, etc., see Figure 4:

[figure not shown]
Steps	Variable assessed	Description
Step 1	Dominance	The weight of individual coronary segments varies according to coronary artery dominance (right or left). Co-dominance does not exist as an option in the SYNTAX score.
Step 2	Coronary segment	The diseased coronary segment directly affects the score as each coronary segment is assigned a weight depending on its location, ranging from 0.5 (i.e. the posterolateral branch) to 6 (i.e. left main in case of left dominance). 
Step 3	Diameter stenosis	The score of each diseased coronary segment is multiplied by two in case of a stenosis 50-99% and by five in case of total occlusion. In case of total occlusion, additional points will be added as follows: 
 – Age >3 months or unknown +1 – Blunt stump +1 – Bridging +1 – First segment visible distally +1 per non-visible segment – Side branch at the occlusion +1 if <1.5 mm diameter +1 if both <1.5 mm and ≥1.5 mm diameter +0 if ≥1.5 mm diameter (i.e. bifurcation lesion)
Step 4	Trifurcation lesion	The presence of a trifurcation lesion adds additional points based on the number of diseased segments: 
 – 1 segment +3 – 2 segments +4 – 3 segments +5 – 4 segments +6
Step 5	Bifurcation lesion	The presence of a bifurcation lesion adds additional points based on the type of bifurcation according to the Medina classification:126 
 – Medina 1,0,0-0,1,0-1,1,0 +1 – Medina 1,1,1-0,0,1-1,0,1-0,1,1 +2 Moreover, the presence of a bifurcation angle <70° adds one additional point
Step 6	Aorto-ostial lesion	The presence of aorto-ostial lesion segments adds one additional point
Step 7	Severe tortuosity	The presence of severe tortuosity proximal of the diseased segment adds two additional points
Step 8	Lesion length	Lesion length >20 mm adds one additional point
Step 9	Calcification	The presence of heavy calcification adds two additional points
Step 10	Thrombus	The presence of thrombus adds one additional point

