4.4.2 Randomization

The randomization will be performed via the Electronic Data Capture (EDC) system hosting the electronic Case Report Form.

In order to ensure balance of the treatment groups across subgroups, we stratified the randomization by site and within site by type of PCI (ad hoc or elective) and the number of vessels to be treated via PCI, i.e., 1, 2, or 3 or more vessel PCI. Within the subgroups we will perform a permuted block design. We will use a block size of 4 patients per block. There will be an equal allocation to the PCI procedure with DCR and the PCI procedure without the use of DCR (1:1 randomization).

In case of elective PCI, randomization will be done before the procedure and in case of ad hoc PCI randomization will be done upon decision to go for PCI right after diagnostics, so when the patient on the table still.

In enrolled subjects the investigator pre procedurally deemed no usage of OCT and/or the rotational or orbital atherectomy is required. During the PCI procedure usage of OCT and/or rotational or orbital atherectomy is left to the investigator's discretion.

In the case OCT and/or rotational or orbital atherectomy is used in enrolled subjects, these subjects will be replaced. When the decision is made to replace a subject this subject will not count for the required total number of subjects total, but will still be part of the Safety population. A new subject will be randomized to either of the arms.

Document ID:	<As applicable, per local requirements>	Document title:		Classification:	For internal use
		Statistical Analysis Plan			
Modified:	11MAY2023	Template ID:	ClinicalStudyTemplate0025	Author:	
Version:	3.0	Template Version Date:	02MAR2018	Approver:	
Status:	Final			Page:	11 of 52

Statistical Analysis Plan

Thus, the following subjects will be replaced:

- Subjects undergoing PCI supported by OCT will be replaced.
- Subjects undergoing PCI supported by rotational or orbital atherectomy will be replaced.

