Version:	3.0	Template ID:	ClinicalStudyTemplate0025	Approver: [REDACTED]	
Status:	Final	Template Version Date:	02MAR2018	Page:	17 of 52

Statistical Analysis Plan

The Chronic Kidney Disease epidemiology (CKD-EPI) equation to estimate the glomerular filtration rate reads [Levey 2009]:

$$eGFR = 141 * \min(SCr/K, 1)^\alpha * \max(SCr/K, 1)^{-1.209} * 0.993^{Age} * 1.018 \text{ [if female]} \times 1.159 \text{ [if black]},$$

with $K=0.7$ and $\alpha=-0.329$ if female;
with $K=0.9$ and $\alpha=-0.411$ if male.

In which SCr is Serum Creatinine. Here min indicates the minimum of SCr/K or 1, and max indicates the maximum of SCr/K or 1.

Based on the eGFR calculation Chronic Kidney Disease (CKD) can be classified in 5 stages [Tsai 2014a].

CKD classification	eGFR (ml/min/1.73m ²)
Stage I (normal renal function)	>=60
Stage II (mild – moderate reduction)	45 – < 60
Stage III (moderate – severe reduction)	30 – < 45
Stage IV (severe reduction)	15 - < 30
Stage V (renal failure)	<15

Table 1 CKD classification based on eGFR

Contrast volume (V) to creatinine clearance GFR ratio

The contrast volume (V)/eGFR ratio will be calculated by dividing the volume of contrast volume (in ml) received by the patients' eGFR (in ml/min/1.73m²).

MACCE

In-hospital Major Adverse Cardiovascular and Cerebral Events (MACCE). MACCE is defined as one or more of the following events: All cause death, Acute Myocardial Infarction (AMI), Coronary Artery Bypass Grafting (CABG), Repeat Coronary Revascularization of the target lesion, Acute Ischemic Stroke (AIS) during hospitalization for the PCI procedure.

Document ID:	<As applicable, per local requirements>	Document title:	Classification:	For internal use
		Statistical Analysis Plan		
Modified:	11MAY2023		Author:	
Version:	3.0	Template ID:	ClinicalStudyTemplate0025	Approver:
Status:	Final	Template Version Date:	02MAR2018	Page: 18 of 52

Statistical Analysis Plan

The **SYNTAX score** [Sianos 2005, Neumann 2018] will be determined for each vessel treated with PCI as an index for anatomical complexity of the PCI, see Figure below and Appendix 1.

The vessel SYNTAX score calculates a point value for each vessel treated with PCI. The patients' overall SYNTAX score will be derived as the maximum value across all treated vessels.

The patients' overall SYNTAX score will be divided into tertiles as an index for complexity of the PCI procedure. We will label these groups as Complexity 1st Tertile, Complexity 2nd Tertile and Complexity 3rd Tertile.

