8.11.3 Exploratory Efficacy Analysis

8.11.3.1 Contrast Volume per Vessel PCI

The average undiluted iodinated contrast volume (in ml) used per vessel PCI (from first positioning the interventional guiding catheter in stable coronary position till end of PCI procedure) by treatment group. For multi vessel PCI the iodinated contrast volume used per vessel PCI will be determined based on the total PCI contrast volume (from first positioning the interventional guiding catheter in stable coronary position till end of PCI procedure) divided by the number of vessels actually treated by PCI.

Descriptive summaries of the total undiluted iodinated contrast volume divided by the actual number of vessels treated by PCI will be presented by treatment group for the FAP and the PP population and will include the number of subjects with non-missing data (n), mean with 95% confidence interval, standard deviation (SD), median, interquartile range (IQR) and minimum and maximum values.

The endpoint will be evaluated using a one-sided two-sample t-test. We will test for assumptions, e.g. normality and equal variances. Normality will be checked using histograms and Q-Q plots. If there are strong indications of non-normality, the data will be (log)transformed, and the back transformed results will be presented. Levene's test for equality of variances will be applied. When the p-value of this test is greater than 0.05, then we assume the variances are equal and we will use the arithmetic mean of the variances in calculating the standard error. When the p-value is less than or equal to 0.05, then we assume

Document ID:	<As applicable, per local requirements>	Document title:		Classification:	For internal use
		Statistical Analysis Plan			
Modified:	11MAY2023	Template ID:	ClinicalStudyTemplate0025	Author:	
Version:	3.0	Template Version Date:	02MAR2018	Approver:	
Status:	Final			Page:	31 of 52

Statistical Analysis Plan

the variances are unequal and then we will calculate the standard error from the weighted average of the two variances.

The results of the t-test will be displayed as estimates of the between treatment group difference (with 95% confidence intervals) and the (one-sided) p-value for the between treatment group difference. When the p-value is lower than the significance level of 2.5% (alpha) we will reject the null hypothesis.

All subjects in the FAP population will be included in this analysis. The analysis will be repeated for the PP population.

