8.14 Adjustment for Covariates

Analyses to determine whether there is an effect based on e.g. intervention difficulty (as measured by the SYNTAX score), lesion characteristics, patient demographics, physician experience, center etc. will be performed. If an effect on the primary or secondary endpoint is found, applying adjustment analysis will be considered. As a sensitivity analysis, we will then perform an analysis

Document ID:	<As applicable, per local requirements>	Document title:		Classification:	For internal use
Modified:	11MAY2023	Statistical Analysis Plan		Author:	
Version:	3.0	Template ID:	ClinicalStudyTemplate0025	Approver:	
Status:	Final	Template Version Date:	02MAR2018	Page:	38 of 52

Statistical Analysis Plan

of covariance (ANCOVA) for the primary and/or the secondary endpoint adjusting for covariates which are deemed important. The results of the ANCOVA will be displayed through Least-Squares Means (LSMEANS) estimates of the between treatment group difference (with 95% confidence intervals) and the p-value for the between treatment group difference adjusted for covariates.

To investigate whether there is a center effect on the primary outcome, we will calculate the Intra Class Correlation coefficient (ICC) of the total iodinated contrast volume between centers. The ICC is the ratio of the variability between centers to the total variance. The ICC measures to what extent the proportion of the total variability of the primary outcome is accounted for by the clustering of patients within centers. If the ICC is higher than 0.10 we will perform a random effects model on the primary outcome with center as a random effect and treatment as a fixed effect. We will also check the distribution of baseline characteristics between centers. If the centers differ in characteristics, which may influence the primary outcome, such as intervention difficulty, lesion characteristics, patient demographics, physician experience etc, we will perform a random effects model on the primary outcome with center as a random effect and treatment and other covariates as fixed effects (ANCOVA) as a sensitivity analysis. The results of the ANCOVA will be displayed through Least-Squares Means (LSMEANS) estimates of the between treatment group difference (with 95% confidence intervals) and the p-value for the between treatment group difference adjusted for covariates.

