12 INDIVIDUAL SUBJECT DATA LISTINGS

STUDY PATIENTS		
Disposition of Patients		
Listing 1	List of Inclusion and Exclusion Criteria	
Listing 2	In- and exclusion criteria	ENROLLED
Listing 3	Randomization results	RAND
Listing 4	Visit Dates	ENROLLED
Listing 5	Study Discontinuation	ENROLLED
Listing 6	Study Completion	ENROLLED
Listing 7	Subjects Analysis Set	SCREENED
BASELINE EVALUATION		
Demographics and Baseline Values		
Listing 8	Demographics	ENROLLED
Listing 9	Medical history	ENROLLED
Listing 10	Medication	ENROLLED
PCI PROCEDURE		
Listing 11	Procedure information	SAF
Listing 12	Procedure and Fluoroscopy time	SAF
Listing 13	Procedure: Contrast Usage	SAF
Listing 14	Procedure parameters	SAF
Listing 15	Procedure: number of runs	SAF
Listing 16	End of procedure information	SAF
Listing 17	Procedural complications	SAF
Listing 18	Procedural comments	SAF
Listing 19	Treated vessel SYNTAX questions	SAF
Listing 20	Number of Vessels treated with PCI and SYNTAX score	SAF
Listing 21	Hospital Discharge	SAF
EFFICACY EVALUATION		
Analysis of efficacy		
Listing 22	Primary and Secondary Efficacy Parameters	FAP
SAFETY		

Document ID:	<As applicable, per local requirements>	Document title:	Classification:	For internal use
Modified:	11MAY2023	Statistical Analysis Plan		
Version:	3.0	Template ID:	ClinicalStudyTemplate0025	Approver:
Status:	Final	Template Version Date:	02MAR2018	Page: 45 of 52

Statistical Analysis Plan

Listing 23	Vital Signs	ENROLLED
Listing 24	Clinical Laboratory Tests	ENROLLED
Listing 25	Major Adverse Cardiovascular and Cerebral Events	ENROLLED
STUDY DEVIATIONS		
Listing 26	Study Deviations	ENROLLED

Document ID:	<As applicable, per local requirements>	Document title:	Classification:	For internal use
Modified:	11MAY2023	Statistical Analysis Plan		
Version:	3.0	Template ID:	ClinicalStudyTemplate0025	Approver:
Status:	Final	Template Version Date:	02MAR2018	Page: 46 of 52

[figure not shown]
Statistical Analysis Plan

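### The SYNTAX complexity score is taken from the vessels actually treated, so the complexity tertiles and any SYNTAX-adjusted sensitivity ANCOVA are not fully protected by randomisation (minor)

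*Protocol*

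**What the plan says.** **Definition of the score.** The exploratory objectives (Protocol 2 and 5.3) use subgroups of simple, intermediate and complex PCI, "where the SYNTAX score for the vessel(s) treated with PCI will be used as an index for complexity". Protocol 7.5, under demographics and baseline characteristics, says that the score "will be determined for the vessel(s) treated with PCI as an index for anatomical complexity", and Protocol 7.8.3 repeats the idea. In SAP 6 the patient's "overall SYNTAX score will be derived as the maximum value across all treated vessels", and the "SYNTAX score will be divided into tertiles as an index for complexity of the PCI procedure". SAP Appendix 1 gives the same rule.

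**Use of the score.** SAP 8.11.3.3 tests contrast volume in each tertile with a one-sided t-test and a 2.5% rejection rule; SAP 8.13 calls the tertile analysis exploratory. SAP 4.5 and 8.14 name "intervention difficulty (as measured by the SYNTAX score") among the factors to be examined. If an effect is found, an ANCOVA is considered as a sensitivity analysis.

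**Timing.** Randomisation is stratified by "the number of vessels to be treated via PCI, i.e., 1, 2, or 3 or more vessel PCI" (SAP 4.4.2). Elective patients are randomised before the procedure, and ad hoc patients once PCI has been decided after diagnostic angiography. The SAP distinguishes this planned count from the realised one: contrast per vessel is total volume "divided by the number of vessels actually treated by PCI" (SAP 8.11.3.1). The listing "Treated vessel SYNTAX questions" stands under the PCI procedure (SAP 12).

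**The concern.** A subgroup factor or covariate is safe in a randomised comparison when treatment assignment cannot change it. SAP 6 defines baseline as the last value before randomisation. A score over treated vessels is known only when the procedure ends, so it does not meet that definition, although Protocol 7.5 files it under baseline characteristics.

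The documents leave a route from arm to score. SAP 4.5 says that the study cannot be blinded. The workflow in Protocol 6.5 allows PCI in a different vessel and leaves deviations to the investigator. The device is expected to save contrast, and both documents cite a contrast-to-GFR benchmark of 3.7. Contrast already used could therefore influence whether a further vessel is treated in the same session.

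If that happened more often in one arm, patients would move between tertiles for reasons linked to allocation. The tertile effects could then show a gradient that is not real. An ANCOVA on the treated-vessel score could also remove part of the contrast difference that arises from treating more or fewer vessels.

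**Working it through.** **1. The plan's own figure.** Inputs from Protocol 7.1: means 152.1 and 129.3 ml (difference 22.8 ml), SD 73.0 ml, one-sided alpha 0.025, power 80%. The standardised difference is 22.8/73.0 = 0.3123. The t-based solution is 161.9, so 162 per arm, and 162/0.9 = 180 per arm. For the secondary endpoint, 177/0.9 = 197 per arm, 394 in total. The primary calculation and both dropout inflations reproduce; the 177 itself was not re-derived. The concern does not change the sample size.

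**2. What is fixed at allocation, and what is not.**

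| Item | Before allocation? | Source |
|---|---|---|
| Lesion anatomy on the diagnostic angiogram | Yes, for both PCI types | Protocol 6.4.1.2; SAP 4.4.2 |
| Number of vessels to be treated | Yes, stratification factor | Protocol 6.1; SAP 4.4.2 |
| Identity of those vessels | Not fixed by the stratum | SAP 4.4.2 |
| Vessels actually treated | No | Protocol 6.5; SAP 8.11.3.1 |
| Patient SYNTAX score as defined | No, follows the row above | SAP 6, Appendix 1 |

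Only departures from the plan arise after allocation. Neither document requires scoring on planned vessels or by a blinded reader; the independent committee in SAP 7 is optional.

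**3. Size under assumed departures.** The documents give no departure rate, so every input marked here is an assumption: 70% planned one-vessel and 30% two-vessel PCI; gamma-distributed vessel scores; volume rising with planned vessel number and score; 40 ml gained or lost per vessel added or dropped. The SD is about 73 ml and the direct device effect 22.8 ml, as in the protocol. Two million patients were simulated per scenario. Entries are control minus DCR in ml, for tertiles 1/2/3.

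| Departure, control vs DCR | Planned-vessel score | Treated-vessel score | ANCOVA, planned vs treated |
|---|---|---|---|
| Higher-score vessel dropped, 10% vs 10% | 23.1/22.6/22.8 | 23.1/22.6/22.8 | 22.8 vs 22.8 |
| Same, 10% vs 5% | 22.3/22.2/22.0 | 23.1/22.3/22.2 | 22.2 vs 22.6 |
| Same, 20% vs 10% | 22.3/21.7/21.2 | 24.0/22.2/21.2 | 21.8 vs 22.5 |
| Same, 20% vs 0% | 21.6/20.0/19.4 | 25.0/20.9/19.6 | 20.4 vs 22.0 |
| Vessel added, 20% vs 0% | 29.3/27.9/27.3 | 26.8/27.3/25.2 | 28.2 vs 26.3 |

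With equal rates the two scores agree within simulation noise. The largest shifts are 25.0 − 21.6 = 3.4 ml in a tertile and 28.2 − 26.3 = 1.9 ml in the ANCOVA. A rerun with another random seed gave the same pattern.

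A second model assumed planned vessels 70/22/8% for 1/2/3, SD about 84 ml, an unplanned vessel in 15% of DCR against 5% of control patients, and no device effect per vessel. Planned-score tertiles were flat at −7.9/−7.7/−8.4 ml; treated-score tertiles read −3.0/−6.8/−9.5 ml. The largest shift is 4.9 ml. The ANCOVA moved from −8.1 to −6.4 ml, a shift of 1.7 ml.

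**4. Against sampling error.** The standard error of a difference is SD × √(2/n per arm), with SD 73 ml.

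- Tertile, n = 54 (162/3): 73 × √(2/54) = 14.0 ml.
- Tertile, n = 66 (about 197/3): 73 × √(2/66) = 12.7 ml.
- Whole trial, n = 177, unadjusted: 73 × √(2/177) = 7.8 ml.

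The largest shifts are thus 4.9/14.0 to 4.9/12.7, or about 35% to 39% of a standard error in a tertile, and 1.9/7.8, or about a quarter, in the ANCOVA. Power for 22.8 ml within one tertile is only 36% to 43%.

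**The case against.** The strongest reply is that the treatment plan is largely set before allocation. The vessel count is a stratum, the diagnostic angiogram is in hand, and lesion anatomy does not depend on the arm. Because the patient score is a maximum, adding or deferring any vessel other than the highest-scoring one leaves it unchanged. All of this stands. A reader might infer that the operator chooses the score after allocation, or that the tertile results are necessarily biased. The documents do not support either reading: only departures from plan are open, and bias needs those departures to differ by arm.

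Nor do the documents suggest an imbalance. The only figures on extent of treatment are mean stent counts in the pilot table of Protocol 7.1.1, 1.76 before and 1.67 after introduction of the device. Stents are not vessels and each group had 21 patients, but nothing there points to more treatment with the device.

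The reply also holds that the SAP wants an index of the procedure performed: it reports SYNTAX under procedure characteristics (8.10) and does not name it among the baseline variables in 8.4. That is a fair reason to report the treated-vessel score. It does not rescue a comparison of arms within groups that the arm can alter.

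Finally, the affected analyses are exploratory or conditional, and SYNTAX is one candidate covariate among several. This limits the severity and is accepted.

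**Conclusion.** The point holds as a minor one. Both documents define the complexity score on treated vessels, and treatment follows allocation in an unblinded trial. The tertile comparisons and any SYNTAX-adjusted ANCOVA therefore lack the full protection of randomisation.

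The size is unknown, because no departure rates are given. It is zero if departures do not differ by arm. Under the assumed imbalances it reaches about 5 ml in a tertile and about 2 ml in the ANCOVA, each below one standard error. These figures concern volume in ml; the ANCOVA of the secondary endpoint and a log-transformed analysis were not simulated.

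A reader might also infer that the main result is compromised. It is not: the primary t-test (SAP 8.11.1) and the secondary Wilcoxon test (SAP 8.11.2) do not use the score.

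**What to change.** - **Definition.** In SAP 6, 8.11.3.3, 8.13, 4.5 and 8.14, define the patient score for the tertiles and the ANCOVA as the maximum over the vessels planned for treatment at randomisation. Score it from the diagnostic angiogram that precedes randomisation; the scoring itself can be done later. Align Protocol 7.5 and 7.8.3.
- **Descriptor.** Keep the treated-vessel score in SAP 8.10 only.
- **Transparency.** Tabulate planned against treated vessels by arm, so that readers can see whether departures differed.
- **Fallback.** Where planned vessel identity was not recorded, adjust the sensitivity ANCOVA for the planned-vessel-number stratum instead, and label the treated-vessel tertiles as conditioned on a post-randomisation variable.

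The cost is changed wording, scoring of the few planned vessels that were not treated, and one eCRF item if planned vessels are not already captured. Protocol 6.5 says that target CAD data and pre-procedural imaging details are entered, so they may be. A new item helps only patients not yet randomised, and the documents do not state enrolment status; the fallback covers the rest. The sample size stays at 394.
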